4.3 Exclusion criteria

- Physical or intellectual impairment precluding informed consent or protocol adherence
- Known pregnancy
- congenital defects with direct impact on central metabolism e.g. amino acid metabolism defect

- uncontrolled diabetes (e.g. HbA1c >11% or Glc >20mmol/l).
- acute or chronic pulmonary disease other than COPD
- renal failure or renal replacement therapy (GFR < 15 mL/min)

4.4 Recruitment, screening and informed consent procedure

Recruitment

COPD patients will be consecutively recruited from the wards at the University Hospital Zurich. The treating physician will approach patients via personal communication. If interested, the treating physician will inform one of the investigators who then will contact the patient.

Participants will not be offered any material compensation for their voluntary agreement to take part in this study (Art. 14 HFG). Whilst the scientific benefit from participation will be explained to participants, no other incentives will be offered.

Patient Information and Informed Consent

The investigators will explain to each participant the nature of the study, its purpose, the procedures involved, the expected duration, the potential risks and benefits and any discomfort it may entail. The right of the participant to refuse to participate without giving reasons will be respected, and withdrawal of consent will not affect the participant's subsequent medical assistance and treatment. In the event of withdrawal of the participant's consent, data collected up to the date of the withdrawal will remain coded in the study database.

The participant must be informed that his/her medical records may be examined by authorised individuals other than their treating physician. The date and time of the consent will be recorded by the investigator (or his designee) and it will be retained as part of the study records.

The participant information sheet and the consent form will be submitted with the protocol for review and approval for the study by the CEC. The formal consent of a participant, using the approved consent form, must be obtained before that participant is submitted to any study procedure.

The participant should read and consider the statement before signing and dating the informed consent form, and should be given a copy of the signed document. The consent form must also be signed and dated by the investigator (or his designee) and it will be retained as part of the study records.

4.5 Study procedures

4.5.1 General study procedures

Upon participation in the study, participants will be requested to answer general questions on their

medical history. The participant will be asked to fill in questionnaires and vital parameters will be determined. Subsequent on-line breath analysis will be performed.

4.5.2 Medical history

General information: age, gender, weight, height, eating habits, activity habits, exacerbation history medication, co-morbidities, smoking history, disease specific images and clinical chemistry test results.

4.5.3 Vital parameters

Vital parameters are measured to reflect the basic function of the human body. We focus on blood pressure and heart rate, which are measured in sitting position after 3 min of rest. Furthermore, temperature and oxygen saturation will be measured.

4.5.4 Inflammatory markers

During the hospitalization of patients with COPD exacerbation blood sampling is routinely performed. CRP level and eosinophil level will be documented for this study during visit 1 and 2.

4.5.5 Spirometry

A spirometry will be performed if the physical state of the patient allows at visit 1 and visit 2. Spirometry results (forced expiratory volume at 1 second [FEV1] and forced vital capacity [FVC]) will be expressed in percentage of predicted values according to the European reference equations.(50) Furthermore a FeNO Test will be used to investigate inflammatory characteristics more in detail. A FeNO Test is routinely performed in asthma patients. The patients should exhale into a to certified sensitive instrument where the NO concentration in the exhaled breath gives conclusion about inflammatory cell lines.

4.5.6 Causative agents

Sputum samples and viral smear is collected routinely during the clinical assessment during hospitalization (visit 1).

4.5.7 Online breath analysis

Real-time breath analysis will be performed with SESI-HRMS. SESI-HRMS is a new developed real time mass spectrometric method besides PTR-MS (51) and SIFT-MS. (52) The big advantage of the SESI method is that the ionisation takes place at atmosphere pressure. This characteristic brings the possibility to connect the SESI ionization source with high resolution mass analyser like the Orbitrap

spectrometer by Thermo Fisher. This results in sensitive and selective, yet real-time, analysis of trace vapour species.(53) Our SESI-HRMS is situated in a separate, lockable room at the University Hospital Zurich. Access to the designated room is only permitted to members of the staff. Participants will be asked to refrain from eating, drinking, chewing gum, alcohol, tobacco, caffeine use or brushing their teeth at least 1 hour before the measurements will be performed. Room temperature and lighting will be set at the same level for all measurements. Participants will exhale through a disposable mouthpiece, into a heated tube (stainless steel, Silconert coated) (50 cm long, 4 mm in diameter) connected to the curtain AUX gas port of a Orbitrap spectrometer (Thermo Fisher, Waltham, Massachusetts, USA) that is provided by DBI. The sampling tube is surrounded with an isolated heating tape at 130 °C to prevent water condensation and to minimize losses of exhaled compounds onto the walls of the tube. While performing full exhalations, the subjects will keep the volume through the sampling line at 8L/min monitored by a digital flow meter. A nano electrospray plume (FIT, Madrid, Spain), provided by DBI, will be used, where compounds of exhaled breath get ionized and subsequently are mass analysed. The technique, by which breath is analysed in real time by injecting exhaled breath into electrospray plumes of pure solvent and thus causing ionization of relevant exhaled compounds(54-56), has been referred to as secondary electrospray ionization (SESI)(57). Breathprints will be collected in real-time recording six replicates through the mouthpiece. The raw mass spectra will be exported as mzXML files for further processing using MATLAB (Mathworks, Inc). The spectra of exhaled breath will be averaged. In this process, only the last few seconds (typically around 6 sec.) of each exhalation will be considered, thus the first part of the exhalation, which reflects mostly the dead space in the upper respiratory tract, will be excluded from the analysis. SESI-MS allows for real-time breath-printing by detection of both volatile and non-volatile trace components in breath without any sample pre-treatment. The de-identified mass spectrometric breath signatures of patients are subsequently analysed by DBI with AI algorithms for spectroscopic profiling.

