2.2 Exhaled breath analysis by mass spectrometry

Analysis of exhaled breath gives biochemical information about the metabolism and the pathophysiological state. Chemical analysis of exhaled breath with mass spectrometry identified numerous volatile organic compounds (VOCs) [low molecular weight-components: < 500 Dalton (Da)].

The origin of these VOCs is diverse. VOCs can either be endogenous (arise from the respiratory tract), systemic (passing the blood-air barrier) or can be of exogenous origin (inhaled/exhaled environment air).⁽²⁾ The alveoli are intimately connected with the systemic circulation through the alveolar capillaries and its large blood-gas-interface. It was demonstrated that exhaled human breath contains a molecular fingerprint (also referred to as breathprint⁽⁹⁾). Breath composition changes during the course of the day (intra-individual variations). These temporal fluctuations may reflect circadian changes (13-15). Despite these changes, it was shown that each individual shows a distinct breathprint stable in time (individual core pattern of volatile and semi-volatile metabolites)⁽¹⁶⁾. The findings of preliminary studies by others and our group suggest that diseases of the airways such as e.g. chronic obstructive pulmonary disease

(COPD)(17, 18) may be diagnosed by a specific exhaled breath pattern.

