2.5 Exhaled breath analysis in COPD

Breath analysis in COPD is attractive because breath is available in nearly unlimited quantities. The analysis is non-invasive, and it presents no burden to the subject being measured. On-line breath analysis in COPD would allow continuous monitoring of metabolic health, disease progression, and medication in short time intervals. Data are obtained immediately which is of high importance in situations like COPD exacerbations.(2)

The diagnostic “gold standard” for COPD is based on spirometry and subjective symptom assessments, similar to asthma with respective COPD guidelines.(29) As it is primarily a disease of the lungs, a high number of breath-analysis studies are available for COPD; however, only a minority of the studies employed on-line methods.(30) Most studies used a case-control design with an untargeted approach in order to identify putative discriminative markers for the disease or disease severity. Three studies used ion mobility separation to identify COPD-specific biomarkers in a cohort of 119, 130, and 96 patients, respectively.(31-33) While two studies reported a 70–79% accuracy in the diagnosis of COPD (based on 6–10 VOCs), the other study reported 10 biomarkers, most of which were unidentified.(31) None of the identified substances overlapped between the two studies or was validated in an external cohort. Finally, two untargeted studies (17, 18) compared the breath print of COPD patients against healthy controls using SESI-MS with a real-time approach. Both studies yielded a Receiver Operating Characteristic (ROC) curve with an area under the curve of 0.88–0.91. However, in this case, with the aid of MS/ MS and complementary pre-separation methods some of the discriminate biomarkers could be identified and attributed to be metabolites of oxidative stress processes, such as fatty acids,

aldehydes, and amino acids.(17, 18) Most studies tried to control for the effects of smoking and there was evidence that lung capacity, body mass index, and certain inflammatory blood markers seem to play a role in the discrepancies observed between groups.(33, 34) In conclusion, studies on this topic are extremely heterogeneous and data processing and statistical methods are not standardized. As a result, none of the reported biomarkers overlaps between the studies and none of the biomarkers has been validated in an external cohort yet.

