4.5.9 Study visits

Participation in the study requires two on-site study visits. Visit 1 will be performed while the participant is hospitalized. This visit will have a duration of approximately 45 minutes. After approximately 8 weeks patients are invited to the hospital to perform visit 2. This visit will take again approximately 45 minutes. Further information in Appendix.

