5. STATISTICS AND METHODOLOGY

5.1 Statistical analysis plan

For data processing, we will follow the same procedure as described in our previous studies [Gaugg, 2016]: raw mass spectra will be transformed to *.mzXML format using the online tool msConvert. The *.mzXML files will be imported into Matlab. Each mass spectrum is then interpolated (shape-preserving piecewise cubic interpolation method), mass calibrated using an iterative grid search algorithm, and the resulting spectra are centroided. To test the hypothesis that there is a significant difference in the values of exhaled metabolites during and after the exacerbation, we will perform a paired-sample t-test to

evaluate differential concentrations of such metabolites. False discovery rate and q-values will be subsequently computed as defined by Storey.(60) To account for instrumental drift (e.g., detector sensitivity), the mass spectra are normalized using standard methods such as interquartile range, total ion current. Well-established data reduction techniques such as principal component analysis will be used for visualization purposes. Finally, high mass resolution/high mass accuracy data obtained will allow us to query online databases (e.g., human metabolome database) to provide tentative identification of the subset of most informative exhaled compounds. The preprocessing of the raw mass spectra and the statistical analysis will be implemented using MATLAB (MathWorks, Massachusetts, US).

For correlation analysis, the Pearson's linear correlation coefficient and 95% bootstrap confidence intervals will be applied. Continuous data will be summarized by means (SD) or medians (quartiles) as appropriate. A two-sided p value of <0.05 will be considered to be statistically significant for all tests.

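### A net change in smoking between the inpatient visit and the 8-week visit cannot be separated from recovery by the unadjusted paired t-test, and the smoking item scheduled at both visits is not used

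*Combined protocol and SAP*

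**What the plan says.** - **Timing (section 4.5.9).** "Visit 1 will be performed while the participant is hospitalized". "After approximately 8 weeks patients are invited to the hospital to perform visit 2". The same section states: "Participation in the study requires two on-site study visits".
- **Place (section 4.5.7).** "Our SESI-HRMS is situated in a separate, lockable room at the University Hospital Zurich". Temperature and lighting are held constant, and only the last seconds of each exhalation are used.
- **Exposure control (section 4.5.7).** "Participants will be asked to refrain from eating, drinking, chewing gum, alcohol, tobacco, caffeine use or brushing their teeth at least 1 hour before" the measurement. The rule is the same at both visits.
- **Eligibility (sections 4.2 and 4.3).** Smoking is not restricted.
- **Data collected (section 4.5.2 and Appendix).** Smoking history is marked at visits 1 and 2. Current smoking and time since the last cigarette are not named.
- **Analysis (section 5.1).** "we will perform a paired-sample t-test to" compare metabolite levels during and after the exacerbation, followed by Storey q-values with no stated cut-off. A two-sided p<0.05 counts as significant for all tests. No covariate and no smoking sensitivity analysis appear.
- **Background.** Section 2.2 accepts that some breath compounds originate outside the body. On earlier COPD breath studies, section 2.5 says: "Most studies tried to control for the effects of smoking".

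**The concern.** Pairing removes whatever is constant within a patient, including being a smoker or a non-smoker. It does not remove an exposure that changes with the visit. Every visit 1 is an inpatient visit with an active exacerbation, and every visit 2 comes about 8 weeks later, so a change in smoking that goes with hospitalisation has the same time pattern as recovery. The 1-hour rule does not equalise smoking before that hour.

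The q-values do not help here. They limit the share of chance findings among ions whose mean does not differ between visits. A tobacco-derived ion whose mean does differ is a real difference to the test, with the wrong cause.

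What is at stake is the label. Section 2.6 hopes to define processes specific to an exacerbation, and section 5.1 sends the most informative compounds on to database identification. If a patient smokes less because of the illness, the resulting ion change is still a tobacco signal and not the biochemistry the study seeks.

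**Working it through.** **The plan's own figure.** The sample size is 40 complete pairs (section 5.2). It was chosen from an earlier study, without effect size, SD or power, so there is no calculation to reproduce. For scale, 40 pairs detect a standardised paired shift of 0.45 with 80% power at two-sided 0.05, whatever its cause.

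**Inputs.** From the documents: n = 40, two-sided 0.05, paired t-test. Assumed, because the documents give none: a share π of patients smokes more before visit 2; a tobacco-only ion shifts by δ log units in them; the other within-pair SD is 0.5; there is no true exacerbation effect.

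**Step 1: unadjusted test.** The paired difference has mean πδ and variance 0.25 + π(1−π)δ². The noncentrality is √40 × mean / SD. For π = 0.20 and δ = 0.5, the mean is 0.10, the variance 0.25 + 0.16 × 0.25 = 0.29 and the SD 0.539, so the noncentrality is 6.325 × 0.10 / 0.539 = 1.17. Simulated rejection rates, with each patient changing independently with probability π:

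| π | δ | mean | SD | noncentrality | P(p<0.05) |
|---|---|---|---|---|---|
| 0.20 | 0.5 | 0.100 | 0.539 | 1.17 | 21% |
| 0.20 | 1.0 | 0.200 | 0.640 | 1.98 | 48% |
| 0.35 | 0.5 | 0.175 | 0.554 | 2.00 | 50% |
| 0.35 | 1.0 | 0.350 | 0.691 | 3.20 | 89% |
| 0.50 | 0.5 | 0.250 | 0.559 | 2.83 | 79% |
| 0.50 | 1.0 | 0.500 | 0.707 | 4.47 | 99% |

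Fixing the number of changers at exactly 20% or 50% gives nearly the same: 20% and 48%, and 81% and 100%.

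**Step 2: stricter cut-off.** At p<0.001 the ranges over δ are about 1% to 6% (π = 0.20), 7% to 37% (0.35) and 25% to 81% (0.50).

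**Step 3: direction.** Only a net change biases the mean. With 20% of patients up and 20% down, the rate at p<0.05 is 5%. With 30% up and 10% down, it is about 18% to 36%.

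**Step 4: q-values.** Assume 1,000 ions, 50 of them true markers shifted by 0.8 SD, and tobacco ions that shift by 2 SD in 12 of the 40 patients. With q<0.05, the share of discoveries not due to the exacerbation is 5% with no tobacco ions, 17% with 20, 31% with 50 and 50% with 100. Errors among ions with no visit difference stay near 5% of discoveries throughout.

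**Step 5: adjustment.** Regress the paired difference on the change in smoking and test the intercept. The rate for a tobacco-only ion returns to about 5% in every scenario, but the simulation supplies the exact indicator that generated the data. If 20% of changers are recorded as unchanged, the adjusted rate is 6% to 28%. If 40% are, it is 8% to 64%.

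**Step 6: precision.** With a yes/no change indicator, the intercept is simply the mean in unchanged patients: 32, 26 or 20 of 40. The standard error rises by √(40/32) = 1.12, √(40/26) = 1.24 or √(40/20) = 1.41. Power for a true shift of 0.45 SD falls from 79% to 70%, 61% or 50%.

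**The case against.** **Measurement place.** A reader might infer that visit 1 is sampled in ward air and visit 2 elsewhere, so that environmental ions in general are at issue. The documents do not support this. Both visits are on site, the instrument stands in one room, and dead-space air is discarded. That patients arrive from home at visit 2 is itself an inference. A smoking covariate would not address exposures shared by all patients. The point is confined to smoking before the measurement.

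**Evidence that smoking changes.** No section gives the share of current smokers or any change between visits. The smoking remark in section 2.5 concerns mainly case-control comparisons between people, which pairing largely handles. This stands: a net change is plausible, not documented.

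**Yardstick.** The 21% to 99% range is per ion at p<0.05. A reader might take it as the error rate of the study's final list. It is not: the plan adds q-values, and Step 2 shows much lower rates at a stricter cut-off. However, section 5.1 fixes no q cut-off and names p<0.05 for all tests, and Step 4 shows that q-values do not remove the confounding.

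**Remedy.** Replacing the primary test by the adjusted intercept would cost real power in an exploratory study of 40 (Step 6), and self-report error leaves some bias (Step 5). Both objections stand, and they argue for a sensitivity analysis. The plan's identifications are also only tentative, which limits the harm.

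**Conclusion.** The point holds in a limited form. The plan allows smoking before the 1-hour abstinence to differ between an inpatient visit and a visit about 8 weeks later, tests the visit difference without adjustment, and makes no use of a smoking item that it schedules at both visits. A net change in smoking is therefore indistinguishable from recovery, and neither pairing nor q-values correct this.

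The size is unknown. The 21% to 99% range rests entirely on the assumed share of changers, shift, SD and a one-directional change; with balanced changes there is no excess. The documents do not show that the bias will occur, only that the analysis could not detect it. This is a worthwhile, inexpensive improvement and not a reason to reject the primary analysis.

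**What to change.** 1. **Data.** Within the smoking item already marked at visits 1 and 2, record current smoking and hours since the last cigarette. Hours since the last cigarette cannot be reliably reconstructed later.
2. **Analysis.** Keep the paired t-test as primary. Add to section 5.1 a pre-specified sensitivity analysis: either regress the paired log difference on the within-patient change in smoking exposure and report the intercept, or restrict to patients with unchanged exposure. With a yes/no indicator these give the same estimate, so they must not be counted as two confirmations.
3. **Labelling.** Flag ions whose estimated visit effect is materially attenuated as possibly tobacco-related, and do not report them as exacerbation-specific. State beforehand what counts as material. Judge by the change in the estimate, because significance can be lost through the smaller effective sample alone.

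The cost is two CRF fields and one extra analysis, with no new procedure for patients. Standard errors in the sensitivity analysis are about 12% to 41% larger if 20% to 50% of patients change exposure, and some confounding remains through self-report error.

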2.4 Exacerbation

An exacerbation of COPD is defined as an acute worsening of respiratory symptoms that results in additional therapy.(24, 25) COPD exacerbations are complex events usually associated with increase in airway inflammation, increased mucus production and marked gas trapping. These changes contribute to increased dyspnea which is the key symptom of an exacerbation.(4)

Exacerbations are classified as:

- Mild (treated with short acting bronchodilators only, SABDs)
- Moderate (treated with SABDs plus antibiotics and/or oral corticosteroids)
- Severe (patient requires hospitalization or visits the emergency room). Severe exacerbations

may also be associated with acute respiratory failure

During a COPD exacerbation, the worsening of the symptoms usually lasts between 7 to 10 days, but some events may last longer. It is well established that COPD exacerbations contribute to disease progression.(26) Disease progression is even more likely if recovery from exacerbations is slow.(27) Exacerbations can also cluster in time and once COPD patients experience an exacerbation, they will show increased susceptibility to further events.(20, 28) Depending on the frequency of exacerbations, COPD patients are divided into infrequent (0-1 exacerbations within the last 12 months) and frequent exacerbators (2 or more exacerbations within the last 12 months). Identifying COPD patients at risk for exacerbations, and especially frequent exacerbations, would be highly desirable to prevent further deterioration of early disease stages.

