3.2.2 Secondary Outcome Measures

Correlation of breath metabolites with symptoms (mMRC and CAT®), inflammation markers (CRP and eosinophils, exhaled NO), causative agents (sputum microbiology and viral swabs) and treatment (inhalational drugs, steroids, antibiotics).

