4.2 Inclusion criteria

- Informed Consent
- Age \geq 18 years
- GOLD stage 2-4, risk groups A-D
- hospitalization due to COPD exacerbation
- Defined exacerbation according to GOLD guidelines
- Subjects adherent to triple inhalational therapy (β -2-sympathomimetics, anticholinergics, steroids)
- Suitable for follow-up assessment
- <48 hours after initiation of antibiotic or steroid impulse therapy

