12. APPENDIX

Overview study procedures

Study Procedure	Parameter Analysis	V 1 (day 0)	V 2 (8 weeks)
ICF		x	
Medical history	age, gender, weight, height, eating habits, activity habits, medication, comorbidities, smoking history, disease specific images and clinical chemistry test results, exacerbation history	x	x
Vital parameter	BP, HR, T, SpO2	x	x
Inflammatory markers	CRP, eosinophil level	x	x
Spirometry	FEV1, FVC	x2	x2
FeNO		x2	x2
Sputum & viral smear		x1	
Observational data collection	On-line breath analysis	x	x
Questionnaire (eg. COPD Assessment Tool)	CAT, mMRC, QUIT	x	x
SE review		x	x

1 collected routinely during the clinical assessment after hospitalization
 
2 if applicable

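### Time since the last inhaled drug is neither controlled nor recorded before breath sampling, and spirometry and FeNO have no fixed place in the visit order, so drug-related ions could be listed as exacerbation metabolites

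*Combined protocol and SAP*

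**What the plan says.** **Control before sampling.** Section 4.5.7 asks participants to "refrain from eating, drinking, chewing gum, alcohol, tobacco, caffeine use or brushing their teeth at least 1 hour before the measurements". No inhaled or other drug is named. The same section limits the analysis to roughly the last 6 seconds of each exhalation, to exclude upper-airway dead space.

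**Inhaled treatment.** Section 4.2 requires "Subjects adherent to triple inhalational therapy", so every participant uses inhalers. Sections 2.4 and 4.1 define an exacerbation by the need for additional therapy. Section 2.4 describes one grade as "Moderate (treated with SABDs plus antibiotics and/or oral corticosteroids" (short-acting bronchodilators, SABDs), but places hospitalised patients, who are the study population, in the severe grade.

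**Recording.** Section 4.5.2 and the appendix collect medication at both visits. Neither asks for the time of the last dose.

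**Order of procedures.** Section 4.5.1 lists history, questionnaires and vital signs, then says "Subsequent on-line breath analysis will be performed". Spirometry and FeNO are not in that sequence. Section 4.5.5 says "A spirometry will be performed if the physical state of the patient allows at visit 1 and visit 2", and the appendix marks both tests with the footnote "2 if applicable" at each visit.

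**Analysis.** Section 5.1 specifies a paired t-test per metabolite followed by Storey q-values, with no covariate and no rule for drug ions. Treatment appears only in the secondary outcomes (section 3.2.2), where metabolites are correlated with "treatment (inhalational drugs, steroids, antibiotics".

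**The concern.** The abstention rule shows that the authors expect recent oral exposures to affect the breathprint. The exposure that eligibility guarantees in every participant is left out. The authors' own background (section 2.5) says on-line breath analysis would allow medication to be monitored, and section 4.5.7 describes an untargeted method that detects volatile and non-volatile compounds.

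If recent inhaled dosing were equally common at both visits, it would add only noise. The two visits differ in setting, however, and visit 1 is by definition a time of additional therapy. A net difference in recent inhaled exposure would run in parallel with the contrast under test. An ion that reflects the drug would then show a real visit difference, pass the q-value threshold for that reason, and be reported among the metabolites of the exacerbation. An unfixed order of spirometry, FeNO and breath sampling leaves open a further, avoidable difference between visits.

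**Working it through.** The plan gives no effect size, SD or power. Section 5.2 states that a conventional sample size calculation is not possible, so there is no figure to reproduce. The calculation below is an illustration only.

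**Inputs from the documents:** 40 complete pairs (section 5.2); two-sided 0.05 and a paired t-test (section 5.1).

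**Assumed inputs, with a range:** SD of the within-pair log difference 0.5; fraction f of patients recently exposed at visit 1 only, 25% to 75%; rise s in a drug-related ion for those patients, 0.3 or 0.7 log units (0.7 is about a doubling). The ion has no biological change.

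**Formulas:**
- mean shift = f × s
- SD = √(0.5² + s² × f × (1 − f))
- noncentrality = (mean / SD) × √40, with 39 degrees of freedom
- chance of p below the threshold from the noncentral t distribution

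**Results per ion:**

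| f | s | mean | SD | noncentrality | P(p<0.05) | P(p<0.001) |
|---|---|---|---|---|---|---|
| 25% | 0.3 | 0.075 | 0.517 | 0.92 | 0.15 | 0.01 |
| 50% | 0.3 | 0.150 | 0.522 | 1.82 | 0.43 | 0.06 |
| 25% | 0.7 | 0.175 | 0.585 | 1.89 | 0.46 | 0.06 |
| 50% | 0.7 | 0.350 | 0.610 | 3.63 | 0.94 | 0.53 |
| 75% | 0.7 | 0.525 | 0.585 | 5.68 | about 1.0 | 0.98 |

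Example for the fourth row: 0.5 × 0.7 = 0.35; √(0.25 + 0.49 × 0.25) = 0.610; 0.35 / 0.610 × 6.325 = 3.63.

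**Does balance remove the problem?** A simulation of 20,000 data sets per scenario expressed the shift in SDs of the paired difference. With no exposure the rejection rate at 0.05 was 5.2%. With exposure at visit 1 only it was 29.1% (f = 25%, 1 SD), 78.7% (50%, 1 SD) and 99.3% (50%, 2 SD). With exposure equally frequent at both visits it was 4.7% to 5.4% for f from 25% to 75% and shifts of 1 to 2 SD. Only the net imbalance between visits matters.

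**Does q-value control help?** No. It limits the share of listed ions that do not differ between visits. A drug ion under imbalance does differ, so it counts as a true discovery of the wrong kind.

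**The case against.** Several points on the other side have force.

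- **End-exhalation sampling.** Using only the last seconds of each breath targets mouth and upper-airway residue and may reduce it. It does not address drug in the lower airways or blood.
- **Maintenance doses.** All participants are meant to be adherent, so a maintenance dose may precede either visit. This stands: the documents do not show how large the imbalance is, or that there is one. A reader might infer that dosing shifts every pair in the same direction. Nothing supports that; at most an unknown fraction is affected.
- **Drug ions can be recognised.** Medication is recorded, and section 5.1 sends accurate masses of the most informative ions to databases. So it would be too strong to say that drug carry-over cannot be told from recovery. What is missing is a rule for acting on a match: the plan promises only tentative identification.
- **Spirometry.** It is planned at both visits under the same condition. That it will precede the breath test at one visit only is a possibility left open, not a plan. A reader might go further and expect effects from propellants, nebulisers, bronchodilators given for spirometry, or ions produced by the forced manoeuvre itself. The documents mention none of these.
- **Short-acting bronchodilators.** The SABD wording in section 2.4 describes mild and moderate exacerbations, while participants are hospitalised and so classed as severe. Their use here is plausible but not stated. The argument rests instead on the definition of an exacerbation by additional therapy.
- **Exploratory study.** This limits the harm of a false lead. The list of ions is nevertheless the main product, and dose timing cannot be reliably recovered afterwards.

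**Conclusion.** The gap is real and narrow. The plan controls food, drink, tobacco, caffeine and tooth-brushing before sampling, but does not record time since the last inhaled drug, fix the place of spirometry and FeNO, or say what happens to ions that match inhaled drugs. Followed exactly, it could list drug-related ions as exacerbation metabolites.

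The size of the bias is unknown. Under the assumptions above, the per-ion chance of a nominally significant result ranges from about 0.15 to about 1.0, against 0.05 with no imbalance. This depends on the assumed SD, on the net fraction exposed at visit 1 only and on the shift. These are per-ion figures; the number of ions affected cannot be estimated from the documents. The documents do not support saying that the primary result is biased, only that the plan could neither detect nor correct such a bias. The changes are worth making because they are cheap and the timing must be captured at the visit.

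**What to change.** In sections 4.5.1, 4.5.7 and 5.1 and in the appendix:

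1. Record drug, device and clock time of the last inhaled dose, and the clock time of the breath test, at both visits. Change no clinical dosing for this purpose. Matching dose intervals between visits should not be required, because it may not be feasible.
2. Perform breath analysis before spirometry at both visits, and give FeNO the same place in the order at both visits.
3. Prespecify that ions matching the known masses of the participants' recorded inhaled drugs are flagged and reported separately from candidate exacerbation metabolites.
4. Add a sensitivity analysis of the primary comparison that accounts for the visit difference in dose-to-breath time, for example as a covariate or in pairs with comparable intervals.

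**Cost:** a few extra CRF entries for each inhaled product at two visits, a fixed procedure order and a mass list. A few genuine ions that coincide with drug masses may be set aside. With 40 pairs, the sensitivity analysis will have limited precision, more so if restricted to a subset.
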